3.1 Inclusion Criteria

At time of registration, patients must have following inclusion criteria:

- 1) Metastatic malignant melanoma, pathologically confirmed
- 2) Age \geq 18 years and ability to provide informed consent
- 3) ECOG Performance Status of 0 or 1
- 4) Patients should be considered good candidates, i.e. ECOG <2 , Creat <2 Bilirubin <2 for conventional high dose IL-2
- 5) No chemotherapy, hormonal therapy, immunotherapy or radiation therapy within 1 month of entry
- 6) Patients with a history or clinical evidence of brain metastasis must have completed radiation therapy or surgical treatment of brain lesions and have no evidence of CNS progression for at least eight weeks at the time of enrollment. Patients must not require corticosteroids for treatment of cerebral edema for brain metastases. Patients must be evaluated with a head MRI within 4 weeks prior to enrollment.
- 7) Patients may have had prior high dose IL-2 or temozolomide but not together or with high dose IL-2 followed by temozolomide
- 8) Patients may have had prior high dose interferon as adjuvant treatment for high risk Melanoma
- 9) Serum Cr < 2 mg/dL
- 10) Bilirubin < 2 mg/dL (except for Gilbert's Syndrome)

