6.0 ASSESSMENTS

6.1 Clinical Assessments

The logistics of the study are summarized in the table, 15.1.8. Patients will be evaluated in the clinic by an investigator before each treatment cycle. Before each cycle of therapy, patients will have routine and correlative science labs performed along with a history and physical examination. These data will be recorded on a form (15.1.4 Clinical Evaluation). An adverse event form will also be completed at each of these evaluations by the study nurse-coordinator (see below). Patients will have staging performed with CT/PET or CT (CAP) after every complete course of treatment (2 complete cycles of HD IL-2 plus 4 weeks of rest plus 3 weeks of oral temozolomide plus 2 weeks of rest prior to reimaging = 1 complete course = approximately 12 weeks). Patients with measurable skin and/or subcutaneous lesions would have 2-dimensional measurements performed using a ruler after each complete course of therapy. They will also have an autoimmune panel drawn after each complete cycle. The autoimmune panel will include an ESR, CRP, ANA, RF, and TSH. Patients with known brain metastases will have repeat MRI of the head after each course. Patients with or without known brain metastases can get repeat MRI at any time should they develop neurologic symptoms as determined by the investigator. Response will be by modified RECIST criteria 1.1 and will employ the following definitions of response:

CR – complete response - no evidence of disease, 100% reduction in the volume of disease

PR – partial response - $\geq 50\%$ but $< 100\%$ reduction in volume of disease

MR – minor response - $\geq 25\%$ but $< 50\%$ reduction in volume of disease

SD – stable disease - $< 25\%$ increase in volume of disease to $< 25\%$ reduction in volume of disease

PD – progressive disease - $\geq 25\%$ increase in volume of disease

The final response will be the best response observed during the course of treatment while on study

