8.0 DATA ANALYSIS AND STATISTICAL METHOD

8.1 Sample Size Determination

The study will employ a Simon 2-stage optimal design with the following specifications: $p_0 = 0.05$, $p_1 = 0.20$, $\alpha = 0.10$, $\beta = 0.10$, where p_0 is the ineffective response rate, p_1 is the effective response rate, α is the false positive rate, and β is the false negative rate. With these specifications, a 2-stage Simon optimal design, which minimizes the expected sample size given an ineffective response rate, will enroll a total of 37 patients with 12 during stage 1 and 25 during stage 2. If there is no response among the first 12 patients, then the drug is considered ineffective and the enrollment will be stopped. Otherwise, the study will proceed to stage 2. The drug will be considered effective if there are at least 4 responses by the completion of the trial.

The design will assure good statistical power with respect to differentiating response rates of 5% and 20% (12). Three additional patients will be enrolled to allow for dropouts to a total of 40.

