8.2 Efficacy Determination

Efficacy analysis will be performed on the intention-to-treat set, which comprises of all patients enrolled in the trial. Patients must have completed at least one complete course (2 cycles) to be considered for response assessment. Patients receiving less than one course will be considered drop-outs from the study in terms of response. Patients who do complete at least one course of treatment will be classified as responders or non-responders. The overall response rate, which is the proportion of the responses among patients in the intention-to-treat set who have completed at least one complete course, will be obtained. In addition, a 95% confidence interval for the overall response rate will be constructed. Responses will be recorded after each course of therapy and will be tabulated as complete response, partial response, minor response, stable disease or progressive disease. Only PR and CR will be included in the numerator of the analysis for overall response but all responses will be recorded. The time to progression (TTP) in months for each patient will be recorded to ascertain the durability of the responses. Waterfall plots for a continuous assessment of response will also be generated. Correlative science results will be studied by non-parametric methods for differences in a given individual over time and between individuals.

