Inclusion criteria - *Subjects must fulfill all inclusion criteria to be included in the study.*

	YES	NO
1. Provision of written informed consent.		
2. Metastatic malignant melanoma, pathologically		
3. Age \geq 18 years and ability to provide informed consent		
4. Patients should be considered ECOG <2 , Creat <2 , Bili <2 for conventional high dose IL-2		
5. No chemotherapy, hormonal therapy, immunotherapy or radiation therapy within 1 month of entry		
6. Patients with a history or clinical evidence of brain metastasis must have completed radiation therapy or surgical treatment of brain lesions and have no evidence of CNS progression for at least eight weeks at the time of enrollment. Patients must not require corticosteroids for treatment of cerebral edema for brain metastases. Patients must be evaluated with a head MRI within 4 weeks prior to enrollment.		
7. Patients may have had prior high dose IL-2 or temozolomide but not together or with high dose IL-2 followed by temozolomide		
8. Patients may have had prior high dose interferon as adjuvant treatment for high risk melanoma		
9. Serum Cr <2 mg/dL		
10. Bilirubin <2 mg/dL (except for Gilbert's Syndrome)		

Exclusion criteria- *The following criteria are considered to be exclusionary for Subjects to be considered for inclusion in the study:*

	YES	NO
1. Inability to provide informed consent.		
2. Hypersensitivity to temozolomide or HD IL-2		

- | | | |
|--|--------------------------|--------------------------|
| 3. Acute gastrointestinal disorders, or cardiac disorders i.e. cardiac failure, MI within 6 months as determined by the investigator |  |  |
| 4. EF < 50% by echo or corrected DLCO < 50% on diffusion capacity testing PFTs |  |  |

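### Measurable disease is not required at entry, so patients who cannot be scored PR may enrol and the planned 90% power is no longer assured; one eligibility line would close the gap

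*Combined protocol and SAP*

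**What the plan says.** Section 3.1 sets the disease requirement as "Metastatic malignant melanoma, pathologically confirmed", and the Appendix I checklist repeats it as "Metastatic malignant melanoma, pathologically". No other inclusion criterion, exclusion criterion or checklist item mentions measurability. The word appears in sections 3.0 and 6.1 only for skin or subcutaneous lesions, where a patient has them.

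Section 6.1 applies a modified RECIST 1.1 in which every category is a change in disease volume. PR is a reduction of at least 50% but less than 100%; MR is at least 25% but less than 50%. The top category reads "CR – complete response - no evidence of disease, 100% reduction in the volume of disease".

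Section 8.2 counts only CR and PR in the numerator. The denominator is the patients who complete at least one course, each classed as responder or non-responder. It gives no rule for a patient whose disease cannot be measured. It adds: "Waterfall plots for a continuous assessment of response will also be generated".

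Section 8.1 sets a Simon optimal design for 5% versus 20% with both error rates at 0.10. The trial "will enroll a total of 37 patients with 12 during stage 1 and 25 during stage 2". It stops if none of the first 12 respond and succeeds with at least 4 responses.

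**The concern.** A percentage reduction in volume needs a quantified baseline. A patient with only non-measurable disease cannot be shown to have a PR or an MR and has no bar in the waterfall plot, but after one course is in the denominator. Unless the disease clears completely, that patient is a non-responder whatever the treatment did. With 37 patients and a threshold of 4 responses, a few such patients lower the chance of recognising an active regimen and raise the chance of stopping wrongly after 12.

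The sample size section makes no allowance for this. Its three extra patients are for dropouts.

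**Working it through.** **Inputs.** From section 8.1: null rate 0.05, target rate 0.20, 12 patients in stage 1 and 25 in stage 2, stop at 0 of 12, success at 4 or more of 37. The share *f* of patients without measurable disease is **not in the documents**; 5%, 10% and 20% are assumptions.

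**Formula.** With response probability *p*, the chance of declaring the regimen effective is the sum over x = 1 to 12 of P(X₁ = x) × P(X₂ ≥ 4 − x), where X₁ is binomial(12, p) and X₂ is binomial(25, p). The chance of stopping at stage 1 is (1 − p)¹².

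**Reproducing the plan, p = 0.20.**
- x = 1: 0.2062 × 0.9018 = 0.1859
- x = 2: 0.2835 × 0.9726 = 0.2757
- x = 3: 0.2362 × 0.9962 = 0.2353
- x ≥ 4: 0.2054

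The sum is 0.902. At p = 0.05 the same formula gives a false positive rate of 0.093. A search over two-stage designs also returns 12/37 with these limits as optimal, so section 8.1 is correct on its own inputs. Power exceeds 90% by only 0.2 points; *f* = 1% in the worst case below already gives 89.9%.

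**Worst case: such patients never respond.** Then p = 0.20 × (1 − f). For *f* = 10%, p = 0.18:

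0.2434 × 0.8533 + 0.2939 × 0.9546 + 0.2151 × 0.9930 + 0.1552 = 0.857; false stop 0.82¹² = 0.092.

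**Milder case: they can still reach CR.** Then p = 0.20 × (1 − f) + 0.20 × c × f, where c is the CR share of responses. Section 3.0 expects 4 responses and 2 CRs in 40 patients on IL-2 alone, so c = 0.5. For *f* = 10%, p = 0.18 + 0.01 = 0.19.

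| Assumed f | p, worst case | Power | False stop, 0/12 | p, c = 0.5 | Power | False stop, 0/12 |
|---|---|---|---|---|---|---|
| 0 | 0.200 | 90.2% | 6.9% | 0.200 | 90.2% | 6.9% |
| 5% | 0.190 | 88.2% | 8.0% | 0.195 | 89.3% | 7.4% |
| 10% | 0.180 | 85.7% | 9.2% | 0.190 | 88.2% | 8.0% |
| 20% | 0.160 | 79.2% | 12.3% | 0.180 | 85.7% | 9.2% |

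The reverse-sequence trial described in section 1.1 gives c = 9.7/16.1, about 0.6. Power is then 88.6% at *f* = 10% and 86.8% at 20%.

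**Stage 1 caveat.** The false-stop columns take response to mean CR or PR. Section 3.0 lets an MR open stage 2, while section 8.1 says only that there is no response. If MR counts and the rate including MR is, by assumption, 25%, the worst-case false-stop risk is (1 − 0.25 × (1 − f))¹² = 3.2%, 3.9%, 4.7% and 6.9% for *f* = 0, 5%, 10% and 20%.

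**False positives under dilution.** With null rate 0.05 × (1 − f), the false positive rate falls from 9.3% to 8.1%, 7.0% and 4.9%. Dilution works against the treatment.

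**The case against.** The best defence is that few unmeasurable patients would enter in practice. Baseline CT or CT/PET is mandatory (sections 3.0 and 5.2), section 5.1 names a RECIST 1.1 measurement form at baseline, and the trial treats metastatic disease. This may well keep the share small, and at 5% the loss is about 2 points at most. But these are procedures, not entry conditions, and good candidacy for IL-2 is defined only by ECOG status, creatinine and bilirubin.

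A second objection is that non-measurable disease that clears can still be a CR. That stands, and it roughly halves the loss.

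Two stronger readings are tempting. A reader might infer that the 90% power is lost. The documents give no share of unmeasurable patients, so they support only that it is not assured.

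A reader might also infer that a patient with fully resected metastases would be scored CR at the first scan and so inflate false positives. Such a patient meets the first half of the CR definition but not the second, because a baseline volume of zero cannot be reduced by 100%. The baseline scan would also show the absence of disease. The miscount is possible but not expected. If one did occur, with all others responding at 5%, the chance of success would rise from 9.3% to 20.5% (that patient in stage 2) or 26.8% (in stage 1). It is a lesser risk, and the same criterion removes it.

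**Conclusion.** The gap holds as a cheap improvement. Eligibility is silent on measurability, the endpoint depends on it, and the analysis has no rule for patients who lack it. The sample size itself is correctly derived.

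The size of the loss rests on an assumed share. It is 1 to 2 points of power at 5%, 2 to 4.5 points at 10%, and 4.5 to 11 points at 20%; the ends of each range depend on whether such patients can still reach CR. The calculation also assumes that all 37 patients complete a course and that measurable patients respond at 20%. The stage 1 figures apply only to the CR-or-PR reading of response.

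**What to change.** Add one criterion to section 3.1 and to the Appendix I checklist, for example: *At least one lesion measurable at baseline under the response criteria of section 6.1, on the baseline CT or CT/PET, or a measurable skin or subcutaneous lesion.* State what counts as measurable under the modified volume criteria, and whether lesions seen only on head MRI qualify. All the imaging is already done at baseline, so no new procedure is needed.

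The cost is an amendment, a few otherwise eligible patients turned away, and possibly slightly slower accrual. The sample size stays at 37.

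If the sponsor prefers to turn no one away, section 8.2 should at least say how patients without measurable disease are scored and counted. That removes the ambiguity but does not restore the power. Dropping four of them from stage 2, for example, leaves 33 evaluable patients (12 still in stage 1) and power of 87.6%.

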also better than those observed when temozolomide was given first and then followed by high dose IL-2 in the UPMC study. We concluded that perhaps the major benefit we observed was a result of the prior high dose IL-2 therapy modulated by the temozolomide and that the sequence of treatment was clearly crucial for this response. We have not observed this effect in 2 patients who received dacarbazine post IL-2. These 2 patients had rapid progressive disease and died.

A possible explanation for this observation entails the T-reg population of lymphocytes (CD4+ CD25+) which act as natural brakes on the immune response and are the main contributors to immunologic tolerance and poor responses to immunotherapy against tumors. They comprise about 2-3% of CD4+ human T-cells. Patients with melanoma typically have high levels of T-reg cells and overactive T-reg cell function (9). These cells act to down-regulate any effective anti-melanoma immune response. Of interest, patients with melanoma who respond to high dose IL-2 have low levels of T-reg cells and their activity. It has been recently demonstrated in animals that low dose continuous temozolomide but not standard dose temozolomide can downregulate T-regs and their function (10). The low dose temozolomide that was given to our patients after they had completed and failed high dose IL-2 is completely compatible to the dosing that was used in this animal study. Based on our clinical experience of an unusually high rate of response in general and CR in particular in patients with melanoma receiving temozolomide post IL-2, we postulate that the temozolomide is acting to inhibit T-reg induction of tolerance resulting in better and somewhat more durable responses. The apparent sequence specific responsiveness noted is satisfactorily explained by this model. We hypothesize that incorporating low dose temozolomide after each cycle of high dose IL-2 for the up-front treatment of melanoma will improve response rate and allow more patients to go to additional course of IL-2 leading to increased CR rate, hopefully many of which will prove to be durable leading effectively to cure of the metastatic disease.

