progression for at least eight weeks at the time of enrollment. Patients must not require corticosteroids for treatment of cerebral edema for brain metastases. Patients must be evaluated with a head MRI within 4 weeks prior to enrollment. Patients may have had prior dacarbazine or temozolomide since the mechanism of action of the temozolomide to be used in the context of this study is related more to effects on immune cells than to its known anti-melanoma effects. Patients would receive baseline staging imaging and laboratory assessment including study-specific immunologic correlative science testing. Patients would receive HD IL-2 according to standard procedure as in-patients on the PSHCI inpatient clinical unit. Patients would receive Cycle 1 of aldesleukin at 600,000 International Units/kg every 8 hours as tolerated up to a maximum of 14 doses. On or about day 10 after discharge from Cycle 1, they would be re-admitted for Cycle 2 of treatment. Then, 28 days after discharge from Cycle 2, they would receive temozolomide at 75 mg/m² daily for 21 days. Two cycles of HD IL-2 therapy as performed above plus 21 days of temozolomide would constitute one course of therapy. After this they would be scanned to assess response with CT/PET or CT(CAP). Responding patients (CR, PR, SD, Minor Response) would be given a 2nd course of treatment as above. Patients with a CR would receive one additional course of treatment and would then be observed. Patients with SD after 2nd course of treatment would go off study. Patients with a PR or Minor Response would continue treatment up to a maximum of 4 courses (8 cycles). If they develop Progressive Disease at any time during this treatment then they would go off study. If they develop a CR then they would have one additional course of treatment provided this course does not make more than 4 total courses. If they have PR or Minor Response after Course 2 then they would receive up to 2 additional courses.

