or MR) then accrual of an additional 25 patients will ensue. Three additional patients would be allowed to accrue to cover any early drop-outs (receipt of less than 2 complete cycles of treatment). Eligible patients would have baseline imaging with CT or CT/PET. A head MRI to rule out asymptomatic occult brain metastases will be performed on all patients as well. Patients with known brain metastases will have baseline MRI done as well and would then have follow-up MRIs performed after each course. An echocardiogram to check cardiac function and PFTs with DLCO will be performed in all patients to assure that they have adequate cardiopulmonary reserve to sustain HD IL-2 as is standard. Patients would have baseline laboratory testing done pre-treatment and at every cycle initiation. An autoimmune panel will be performed pre-treatment and after every cycle of treatment. Correlative science immunoassays will be performed pre-treatment and after every cycle of treatment. Response as per radiologic imaging assessment and physical assessment of accessible and measurable skin metastases if applicable will be performed after every course of treatment (2 cycles HD IL-2 and 21 days of temozolomide.). Response will be determined after course 1 of treatment as a complete response (CR), partial response (PR), minor response (MR), stable disease (SD) or progressive disease (PD) according to standard definitions of response. Patients with CR will receive another complete course of treatment and will then go off study except for follow-up. Patients with progressive disease (PD) will go off study after course 1. Patients with stable disease (SD) after course one will repeat one additional course maximum. Patients with PR or MR will continue with additional courses as determined by response up to a maximum of 4 courses total (8 cycles). Responses and their durability will be compared to known rates of response and their durability using HD IL-2 alone. For a population of 40, using standard HD IL-2, the expected response rate 10% would be in 4 of the 40 and the CR rate 5% in about 2 of the 40. We would hypothesize that we can at least double these at a minimum using the methods described in this protocol.

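### No progression is required after prior therapy, so residual shrinkage from it can count as a study response if it reaches a further 50%; the pretreated population is also described inconsistently

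*Combined protocol and SAP*

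**What the plan says.** **Eligibility.** Inclusion criterion 7 in section 3.1 reads "Patients may have had prior high dose IL-2 or temozolomide but not together or with high dose IL-2 followed by temozolomide". Criterion 5 sets the interval: "No chemotherapy, hormonal therapy, immunotherapy or radiation therapy within 1 month of entry". Neither asks how the earlier treatment ended. Elsewhere in 3.1, 3.2 and the Appendix I checklist, progression appears only as the absence of CNS progression in patients with treated brain metastases. Measurable disease is not required.

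**Population.** The hypothesis in section 1.2 is that "incorporating low dose temozolomide after each cycle of high dose IL-2 for the up-front treatment of melanoma will improve response rate". The synopsis (1.3) says "Patients may have had prior dacarbazine or temozolomide since the mechanism of action of the temozolomide to be used" and does not mention prior HD IL-2. Section 3.1 does.

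**Response.** Baseline imaging is done within 28 days (5.2: 4 weeks) before treatment, and restaging follows each course of about 12 weeks. Section 6.1 defines PR as a volume reduction of at least 50% but under 100%, MR as 25% to under 50%, and SD as a change under 25% either way. The best response on study is the final one. Section 8.2 puts only CR and PR in the numerator.

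**Decision rule.** Under section 8.1 the trial "will enroll a total of 37 patients with 12 during stage 1 and 25 during stage 2". It stops early on this rule: "If there is no response among the first 12 patients, then the drug is considered ineffective and the enrollment will be stopped". Four responses make the regimen effective.

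**Comparison.** Section 3.0 plans: "Responses and their durability will be compared to known rates of response and their durability using HD IL-2 alone".

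**The concern.** A patient can enter a month after HD IL-2, temozolomide, other systemic therapy or radiation while the tumour is still shrinking. If treatment starts promptly, a scan taken up to 28 days earlier can fall within days of the last prior dose. Much of the late effect of that therapy could then lie between the baseline scan and the first restaging. The plan has no rule for deciding which treatment caused the shrinkage, and it has no rule for lesions irradiated shortly before entry.

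The conclusion rests on four responses, so one misattributed response is a quarter of what is needed.

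Separately, a mix of HD IL-2-naive and HD IL-2-treated patients is to be set against historical results of HD IL-2 alone. The protocol does not say which patients that comparison concerns.

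**Working it through.** **Inputs from section 8.1:** null rate 0.05, target rate 0.20, 12 patients then 25, stop at 0 of 12, effective at 4 or more of 37. I take 37 evaluable patients and count CR and PR in both stages. Section 3.0 also lets an MR open stage 2; on that wording less residual shrinkage is enough to continue.

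**Step 1: reproduce the plan.** With X ~ Bin(12, p) and Y ~ Bin(25, p), P(effective) = Σ over x ≥ 1 of P(X = x) × P(Y ≥ 4 − x). At p = 0.05:

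- x = 1: 0.3413 × 0.1271 = 0.0434
- x = 2: 0.0988 × 0.3576 = 0.0353
- x = 3: 0.0173 × 0.7226 = 0.0125
- x ≥ 4: 0.0022

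The total is 0.0935 before rounding of the terms, within the 0.10 ceiling. At p = 0.20 the same sum gives 0.902. A search for the smallest expected sample size returns the same 12 + 25 design, so the sample size is correct.

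**Step 2: one carry-over patient.** Replace one of the 37 with a patient whose chance of scoring PR or CR from earlier therapy is q, and keep the rest at 5%. Then P(effective) = q·A + (1 − q)·B. A is the probability of declaring efficacy if that patient responds, and B is the probability if not. Exact values are A = 0.2679, B = 0.0843 for a stage 1 patient and A = 0.2053, B = 0.0876 for a stage 2 patient. As a check, q = 0.05 returns 0.0935 in both cases (0.0134 + 0.0801; 0.0103 + 0.0832).

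| Assumed q | Stage 1 | Stage 2 |
|---|---|---|
| 0.10 | 0.0268 + 0.0759 = 0.103 | 0.0205 + 0.0788 = 0.099 |
| 0.25 | 0.0670 + 0.0632 = 0.130 | 0.0513 + 0.0657 = 0.117 |
| 1.00 | 0.268 | 0.205 |

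Two certain carry-over responders give 0.355 if both are in stage 2 and 0.528 if at least one is in stage 1. That is the upper end.

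**Step 3: the opposite effect.** The same criterion admits patients who failed HD IL-2. Suppose six of the 37 (two in stage 1, four in stage 2) have a 2% response rate and the rest 5%. P(effective) falls to 0.070. Making one of the remaining stage 2 patients a carry-over patient with q = 0.25 brings it to 0.090, still below 0.10.

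The number of carry-over patients, q, the six patients and the 2% are all assumptions. The documents give no share of pretreated patients and no rate of late shrinkage.

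**Step 4: the population, side by side.** Section 1.2 speaks of up-front treatment, 1.3 of prior dacarbazine or temozolomide, and 3.1 of prior HD IL-2 or temozolomide. The five patients who prompted the trial had failed HD IL-2, but failure is not an entry condition.

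**The case against.** The best defence is that imaging is reset at entry. A reader might infer that any further shrinkage at the first restaging scores as PR. Section 6.1 does not support that: the volume must fall at least 50% from the new baseline. Lesser shrinkage is MR or SD, neither of which enters the numerator in 8.2. This stands, and it confines the problem to patients with substantial further shrinkage or no remaining disease. It does not remove the problem, because the new baseline may itself be close to the last prior dose.

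A reader might also take section 1.2 as crediting later responses to earlier IL-2 alone. It does not. It suggests, with a hedge, a benefit of prior IL-2 as modulated by temozolomide, in patients who had failed IL-2. That is the trial's own hypothesis and no evidence of late shrinkage after IL-2 alone.

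Nor does the synopsis bar prior HD IL-2. Its sentence is permissive, so criterion 7 adds to it without contradicting it. Criterion 7 also excludes patients who have already had the study sequence, which is a real safeguard.

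Finally, steps 2 and 3 pull in opposite directions, so inflation of the false-positive rate is possible but not established. That stands too.

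**Conclusion.** The gap holds in a limited form. Nothing in the eligibility criteria or response rules prevents a carry-over response from counting towards the four, provided it clears the 50% threshold or leaves no disease. For one such patient the false-positive rate moves from 9.3% to between 9.9% and 27%, depending on the assumed chance of response and the stage of entry. With a modest chance of response the change is small.

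The net bias cannot be signed from the documents. One might conclude that the comparison with HD IL-2 alone is uninterpretable, or that the historical rates come from a different population. The documents do not show either: they quote those rates without stating prior treatment. What they do show is that prior HD IL-2 is handled differently in 1.2, 1.3 and 3.1, and that no analysis by prior HD IL-2 status is planned.

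This is an inexpensive improvement to the design. It does not challenge the sample size.

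**What to change.** 1. **Section 3.1 and Appendix I.** For patients with prior systemic therapy for metastatic disease, require documented progression since that therapy, at or before the baseline scan. Do not count previously irradiated lesions towards response unless they have progressed since. State that patients with treated, stable brain metastases under criterion 6, and patients with local radiation and unirradiated disease elsewhere, remain eligible.
2. **Sections 1.2, 1.3 and criterion 7.** Reconcile them so that they say the same thing about prior HD IL-2.
3. **Section 8.2.** Keep the overall 4-of-37 rule. Report the response rate with its 95% confidence interval by prior HD IL-2 status (naive or treated), and base the descriptive comparison with HD IL-2 alone on the naive group.

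The cost is one eligibility criterion with its checklist line, some reconciled wording and one table. Stage sizes, the nominal false-positive rate (0.0935) and power (0.902) are unchanged. Accrual may be slightly slower, and the interval for the naive subgroup will be wider than for the whole trial; the documents do not allow either to be quantified.
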